[figure not shown]
Official Title:	Mobile Health Obesity Wellness Intervention in Rural Older Adults (MOWI): Home-Based Pilot
NCT number:	NCT03104205
Document Type:	Study Protocol and Statistical Analysis Plan and Informed Consent Form
Date of the Document:	July 3, 2018

Overview: The study will: 1) Obtain input on feasibility, usability, and acceptability of using mHealth in behavior change by adapting a device for rural older adults; 2) Develop, refine and tailor MOWI in research settings; 3) Conduct MOWI in subjects' homes. The overall goal is to improve older adult physical function in rural areas and use the results as a basis for an R01 randomized trial testing the MOWI's delivery in the home.

Study Setting/Population: Dartmouth-Hitchcock (D-H) serves 1.5 million persons from a circumscribed area of rural New Hampshire/Vermont. The site of Lebanon, NH, is a typical rural New England town (16.2% aged ≥65 years; 95.4% Caucasian⁸³). Of 13,293 primary care patients ≥65 years old at D-H, 3,987 are study eligible (~30% obese⁸⁴). The Center for Health & Aging (CHA) has rooms for study assessments. In-home evaluations will use CHA video equipment.

Recruitment: As a Geriatrician working with an interdisciplinary team, I have ready access to potential subjects from a practice panel of ~3000 older adults. In addition the Centers for Health and Aging provide a venue for recruitment, as indicated by successfully recruiting 111 elderly subjects this past year for pilot studies by 3 junior faculty. Patients meeting study criteria will be identified using record review and e-mailed/mailed letters describing the study (after HIPAA waiver). Posters/handouts will be placed strategically at D-H. Colleagues will give information materials to patients requesting permission for contact by the study research assistant. With respect to the qualitative component, the PI will recruit 6 clinicians (from 87 in the provider network) to participate in interviews. [name] will use the CHA's extensive aging services network to recruit 4 leaders of aging services organizations for study participation.

FIGURE 2: STUDY OVERVIEW

Selection Criteria: Focus groups, interviews, and usability testing will target English-speaking obese older adults (age ≥65 years and BMI ≥30kg/m²¹⁷ or waist circumference ≥88/102cm⁸⁵ in females/males). Excluded from eligibility are adults with severe mental or life-threatening illness, dementia, substance use, history of bariatric surgery, suicidal ideation, unable to provide consent/perform measures, or residing in a nursing home. Older adult participants in Aims 2 & 3 will require the presence of home Wi-Fi high-speed internet, medical clearance, have less than a 5% weight loss in the past 6 months, and be without advanced co-morbidity, exercise restrictions⁸⁸ or involvement in other research studies.

Screening/Consent: Subjects expressing interest will be mailed/mailed forms, evaluated by chart review to confirm eligibility, and those meeting criteria invited to an RA-led session to verify final eligibility, review and complete consent forms, and answer queries. Competence for consent will be assured by: no diagnosis of dementia (all Aims) and a Callahan score ≥4 (Aims 2 & 3). Written consent will be obtained before enrollment. The RA will obtain screening/baseline measures, and provide a list of contact details (see Human Subjects).

10. Aim 3 (Evaluate home-based MOWI): Conduct and assess the feasibility, acceptability, and potential effectiveness of a home MOWI: MOWI will be delivered via video-conferencing in the subject's home in a 3x per week, 26-week program from the CHA (in contrast to Aim 2) by: an individual dietitian-led weekly nutrition session; 2x/week physical therapist-led group exercise session⁶⁹; and Fitbit monitoring of activity. We plan 5 cohorts of 8 subjects n=40. In-person RA-led assessments will occur at 0, 4, 8, 12 and 26 weeks. Only one exercise session will occur during these weeks. A HIPAA-compliant Android tablet with video-conferencing software (Vidyo)¹²⁰ will be configured by the Telehealth team and can record sessions, allowing 10% to be viewed randomly by the PI for fidelity. Prior to each nutrition session at home, weight will be assessed using a Bluetooth scale.

MOWI Consists of the following: a 12-week, 3x/week program of: weekly nutrition counseling; 2x/week group exercise visits; and Amulet to monitor activity, strength, and gait speed. A dietitian and physical therapist will lead the in-person (15-20 min) nutrition and exercise (70-90 min) sessions. The team will provide advice and troubleshooting of each element. Two waves of 8 individuals each will be assessed at 0, 4, 8 and 12 weeks and be given Amulet. Further, Amulet/Fitbit will measure steps, activity type, duration and distance.

A 2x/week, physical therapist-led guideline-based exercise regimen⁸⁸ will be held at CHA focusing on progressive resistance, flexibility, balance and aerobic exercise at moderate intensity to improve strength,

quality, and mobility¹¹³. Adjustable cuff weights and Thera-bands will be given for upper/lower limb exercises. Resistance training will target major muscle groups⁸⁸ (30-45min, 3 sets, 8-12 repetitions). After 15 repetitions of full range of motion, loads will increase, followed by flexibility exercises (15-30min) of static stretches (30-60s). Neuromotor training will focus on agility, balance, and coordination, including static, dynamic, vestibular and Tai Chi (15-30min). Subjects will be trained to perform exercises 1-2 days/week and educated in aerobic activity (30min/day, minimum 10min bouts, 150min/week^{88,114,115}) outside the sessions. Baseline personalized plans will be created aimed at gradual workload increases. Individual weekly dietitian counseling sessions¹¹⁶ at the CHA. will consist of behavioral modification¹¹⁷ and motivational interviewing¹¹⁸ based on the 5 A's.^{91,119} The initial visit is the basis for an individualized program using a point-of-care 24-hour diet recall¹²⁰, reducing recall bias, and avoiding the burden and non-adherence of self-reported, home-based measures. Elements include: caloric restriction (500-750 kCal/d); high protein (1-1.5g/kg /day)^{94,121,122}; 800IU vitamin D^{123,124} and weekly weigh-in¹²⁵. This approach counters weight loss induced sarcopenia and bone loss^{88,89,107,108}.

I will conduct a usability evaluation consisting of individual semi-structured interviews, interview and satisfaction questionnaires, repeating the process after the 2nd wave. The RA will record and transcribe all sessions allowing me to discuss these with my team. Outcomes and analyses are detailed below.

STATISTICAL DESIGN AND POWER

Aim 1 (*Qualitative assessment*) will use mixed-methods to adapt Amulet and MOWI for use in rural older obese adults. Aim 2 (*Develop/refine MOWI*) and Aim 3 (*Evaluate home-based MOWI*) will explore feasibility/acceptability, and preliminary effectiveness of the above outcomes. Data will be analyzed as follows:

Aim 3 (Evaluate home-based MOWI): Conduct and assess the feasibility, acceptability, and potential effectiveness of a home-based MOWI:

- Feasibility/Acceptability: Rates of screening, eligibility, enrollment, completion, assessment, entry criteria
- suitability, attrition reasons, satisfaction, acceptability, usability, and feasibility of MOWI will be assessed using mixed-methods at 26 weeks as in Aim 2.
- Statistical Analysis: The 1^o outcome of Physical Function and 2^o outcomes of behavioral activation, health status, and activity will be assessed and analyzed at 0, 4, 8, 12, 26 and 12-weeks post-study as in Aim 2.
- Sample Size & Power: We intend on enrolling 40 subjects. The sample size undergoing the intervention by the team is manageable allowing us to detect with 80% power at a 5% type I error rate, an effect of MOWI that improves grip strength in 70% using a binomial test. More efficient approaches such as Wald tests of the time term from a mixed effects model with random intercept (or generalized estimating equations with patient cluster) for patient will detect an effect equal to 0.6 within subject standard deviations (0.8 standard deviations of change from baseline), calculated using the Monte Carlo method. We will estimate correlations between pre/post-measures, or equivalently, the partitioning into between subject and within subject variation, which are also essential for randomized trial power calculations. We emphasize Aim 3 is not designed to definitively provide evidence for a treatment effect, but designed to inform a comprehensive, larger study and whether it should be conducted.

Recruitment and Retention Strategies

Participants will be recruited from referrals from Family Medicine/General Internal Medicine providers (Primary Care), providers from the Dartmouth Weight & Wellness Center, and community members attending the Dartmouth Center for Health and Aging (DCHA). I will inform clinicians of Family Medicine and General Internal Medicine and the staff at the Weight & Wellness Center of the proposed study during section meetings. [name] has an extensive network of community-care providers and will send e-mails/letters to the CHA's listserv and mailing list requesting participation. Posters will be placed in each examination room, in the patient waiting areas and in common areas of the DCHA. All posters will have been pre-approved by DHMC patient/family advisors and the Committee for the Protection for Human Subjects. Additionally, postings in the DCHA quarterly newsletter, the DHMC weekly D-H Today online bulletin, the weekly Geisel School of Medicine at Dartmouth newsletter, and electronic mailing lists will promote the study. We anticipate advertising in the local newspaper as well. A dedicated phone number and e-mail will be assigned to this study.

Patients will be identified from the PI's clinical practice group at D-H, word of mouth, or other means as indicated below. We will also identify prospective individuals fulfilling basic eligibility criteria after obtaining a HIPAA waiver for electronic record review from the Committee for the Protection of Human Subjects. A pre-assessment eligibility would be performed to limit the burden on patients should they be ineligible after full informed consent for the requisite aims. This will allow the investigators to query our electronic medical record and if necessary send targeted messages and/or letters to individuals that may possibly qualify for this study. If needed, the study staff will send a letter to prospective individuals requesting their involvement either by mail or email (through the electronic medical record). This letter will describe the study and provide contact information for those interested. The CTO will also have details of the study. Any individuals that have expressed interest will be contacted by the team by phone or by email which will be the most preferable method of communication. A pre-screening questionnaire or electronic link to RedCAP (See below) or by phone will be mailed/mailed to participants (depending on patient preference).

As part of Aim 1a, eligible patients will be asked to participate in qualitative focus groups and individual semi-structured interviews with a member of the team. It is anticipated that the focus group will occur 4-6 weeks after interest is expressed. The investigators will perform four separate patient focus groups. Semi-structured interviews will take place for clinicians and community leaders of health and senior centers. At the time of communication, the consent form will be sent to these individuals for review (paper or electronic) and if they agree to the terms of the consent, the individuals will attend these sessions at a mutually convenient time for the study participants and the Research Team. A reminder letter will be sent either via myDH (through the electronic medical record) by the PI, and/or a hard copy letter to the patient's address.

As part of Aim 1b, eligible patients will be asked to attend the DCHA to confirm eligibility and informed consent process by the RA/PI (See Section on *Informed Consent Procedures* for Full details). Those ineligible will be informed by the team and any information will be destroyed. We anticipate that eligibility to study onset will be roughly 4-6 weeks after screening.

As part of Aim 2 and 3 (including the pre-pilot Aim 2), eligible patients will be asked either to attend a baseline visit with the RA or PI at the DCHA to confirm study full eligibility for measurements and full informed consent process by the RA/PI (See Section on *Informed Consent Procedures* for Full Details). Those ineligible will be informed by the team and any information will be destroyed. We anticipate that eligibility to study onset will be roughly 4-6 weeks after screening. The patient's primary care provider will provide medical clearance prior to study enrollment and sign a paper or electronic form allowing the individual to undergo this intervention. They will be kept informed of any abnormal symptoms or problems throughout the study.

The investigators recognize that this intervention may lead to attrition. To reduce the risk of participant drop-out, participants will be reminded of sessions with a phone call, e-mail, and Amulet messaging reminder from the RA. Individuals will be compensated with sandwiches/snacks plus \$25 gift card for the focus groups of the qualitative aim (Aim 1a), \$25 gift card for the subject semi-structured interviews, a nominal \$10/hour payment for the prevalidation phase of Aim 1b (cash, gift-card), a \$25 gas card each for Aim 1b, \$100 for completing >80% of the visits and assessments for the three-month program (Aim 2) - \$25 per assessment, and \$200 for completing >80% of the visits and assessments at 6-months (Aim 3). Payment will be made at study conclusion according to institutional policies. They will also receive a fixed schedule of items (pens, notepads, thank you cards) to recognize their participation to date. Participants will have the option of declining such incentives at any time. We will provide a \$25 gas card or equivalent for each visit (Aim 4).

No involvement of special vulnerable population such as fetuses, neonates, pregnant woman, children, prisoners, institutionalized individuals or others who may be considered vulnerable will be included in this study. The study will be a single-arm study and there will be no assignment to a study group for this study.

Retention

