visits. If an SAE occurs, the PI will report the event to the Dartmouth CPHS using the CPHS Adverse Event Form, to the DSMB, and to the NIA Program Officer within 10 days of the study's knowledge of the SAE (if unanticipated) unless otherwise requested by the DSMB. The PI, in consultation with co-investigators and others, as needed, will review the adverse event report and gather other information as needed to investigate the event and determine the need for subsequent action. Any subsequent action will be documented and reported to the CPHS. In addition, any SAE will also be reported to the NIH program officer and they will be informed of any actions taken by the CPHS as a result of its continuing review. The CPHS will review each reported adverse event to determine whether: the participants in the study should receive additional information related to continuing their participation; the protocol, study plan or consent form should be modified; or the study should be temporarily suspended. If the CPHS determines that some action in response to the adverse event is necessary, the CPHS will promptly inform the PI. All deaths will be reported in an expedited manner, normally within 24 hours of the study's knowledge. The report of death will also be submitted to the NIA Program Administrator and to the CPHS and to the DSMB Chair.

STATISTICAL DESIGN AND POWER

Aim 1 (*Qualitative assessment*) will use mixed-methods to adapt Amulet and MOWI for use in rural older obese adults. Aim 2 (*Develop/refine MOWI*) and Aim 3 (*Evaluate home-based MOWI*) will explore feasibility/acceptability, and preliminary effectiveness of the above outcomes. Data will be analyzed as follows:

Aim 3 (Evaluate home-based MOWI): Conduct and assess the feasibility, acceptability, and potential effectiveness of a home-based MOWI:

- Feasibility/Acceptability: Rates of screening, eligibility, enrollment, completion, assessment, entry criteria
- suitability, attrition reasons, satisfaction, acceptability, usability, and feasibility of MOWI will be assessed using mixed-methods at 26 weeks as in Aim 2.
- Statistical Analysis: The 1^o outcome of Physical Function and 2^o outcomes of behavioral activation, health status, and activity will be assessed and analyzed at 0, 4, 8, 12, 26 and 12-weeks post-study as in Aim 2.

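### If participants change at different rates and time is fitted as a linear term, the random-intercept model's standard error is too small and its Wald test exceeds the nominal 5%

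*Combined protocol and SAP*

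**What the plan says.** The combined protocol and SAP, under STATISTICAL DESIGN AND POWER, Aim 3, Sample Size & Power (printed twice with the same text), plans 40 participants and aims to "detect with 80% power at a 5% type I error rate". It first gives a binomial test on grip strength. It then offers, as examples of more efficient approaches, "Wald tests of the time term from a mixed effects model with random intercept" ("or generalized estimating equations with patient cluster"). The detectable effect is put at 0.6 within-subject SDs, from a Monte Carlo calculation whose inputs are not shown. The only variance components mentioned are between-subject and within-subject.

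Under Statistical Analysis, the primary and secondary outcomes "will be assessed and analyzed at 0, 4, 8, 12, 26 and 12-weeks post-study as in Aim 2". The Aim 2 analysis that this refers to is not in the document. No random slope, type of standard error, small-sample correction, coding of time or sidedness is given. The same section says that Aim 3 is not meant to give definitive evidence of an effect, but to inform a larger study and whether to run it.

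**The concern.** A random intercept lets participants start at different levels but makes them all change at one rate. The model then treats a person's departure from the common slope as independent visit-to-visit noise. It is not: someone who responds faster than average departs from the common line systematically, and extra visits do not average that away.

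Equal rates are doubtful here. The intervention description has exercise plans tailored at baseline, an individualised diet programme and unsupervised exercise between sessions, and Aim 3 delivers the programme at home for 26 weeks. If rates differ, the interval for the time effect is too narrow and the test rejects more often than 5%. At stake is the quality of the evidence that Aim 3 passes to the decision on the larger trial.

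**Working it through.** **Inputs.** From the plan: n = 40, 5% type I error, 80% power, visits at weeks 0, 4, 8, 12 and 26, and a visit 12 weeks post-study (26 + 12 = week 38). Assumed, because the plan does not say: two-sided test, linear time, complete data, and independent normal visit errors with SD 1 (so the unit is the within-subject SD). Individual slopes have SD τ per week, with 26τ set at 0.25, 0.5, 1.0 and 1.5.

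**Step 1: the plan's 0.6.** Let S be the sum of squared centred visit times and L the time span. With no slope variation, the detectable change over L is (1.96 + 0.8416) × L / √(nS).

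- Visits 0-12: S = 80; 2.8016 × 12 / √3,200 = 0.594 (power at 0.6: 80.7%).
- Visits 0-26: S = 400; 2.8016 × 26 / √16,000 = 0.576 (power at 0.6: 83%).
- Visits 0-38: S = 1,053.3; 2.8016 × 38 / √42,133 = 0.519 (power at 0.6: 90%).

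So 0.6 is reproduced on the first two schedules when all participants share one slope.

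**Step 2: the two variances.** With balanced data the estimated time effect is the mean of the participants' own least-squares slopes. Put x = τ²S and let J be the number of visits.

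- True variance: (1 + x) / (nS).
- Variance used by the random-intercept model: [1 + x(n − 1)/(n(J − 1) − 1)] / (nS), because the slope deviations are spread over all the residual degrees of freedom.
- R = √(model variance / true variance), and two-sided type I error = 2Φ(−1.96R).

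**Step 3: numbers at 26τ = 1.0.**

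- Five visits: x = 400/676 = 0.592; model 1 + 0.592 × 39/159 = 1.145; true 1.592; R = 0.848; type I error 2Φ(−1.662) = 9.6%.
- Six visits: x = 1,053.3/676 = 1.558; model 1 + 1.558 × 39/199 = 1.305; true 2.558; R = 0.714; type I error 2Φ(−1.400) = 16.2%.

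| Assumed slope SD over 26 weeks | Visits 0-26, formula | Visits 0-26, simulated | Visits 0-38, formula | Visits 0-38, simulated |
|---|---|---|---|---|
| 0.25 | 5.3% | 5.4-5.5% | 5.9% | 6.1-6.3% |
| 0.5 | 6.3% | 6.2-6.4% | 8.5% | 8.5-8.8% |
| 1.0 | 9.6% | 9.8-10.2% | 16.2% | 16.1-16.7% |
| 1.5 | 13.9% | 13.4-14.4% | 23.0% | 23.0-24.6% |

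In the simulations about half of the false rejections were towards improvement. On visits 0-26 at slope SD 1.0 that is about 5%, against a nominal 2.5% per tail. A t test on participant-level slopes stayed at 4.5-5.5%, and GEE with an uncorrected robust variance at 5.5-6.7%. Results at n = 27 (about half of the planned 53 recruits) were similar.

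**Step 4: coding of time, at 26τ = 1.0.** With categorical time, the week 26 versus week 0 contrast has true variance (2 + 1)/n. The model uses 2(1 + x/(J − 1))/n.

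- Five visits: 2(1 + 0.592/4) = 2.296; R = √(2.296/3) = 0.875; type I error about 8.6% (simulated 8.7-8.9%).
- Six visits: 2(1 + 1.558/5) = 2.623; R = √(2.623/3) = 0.935; about 6.7% (simulated 6.4-6.9%).
- Week 38 versus week 0: true 2 + (38/26)² = 4.136; R = √(2.623/4.136) = 0.796; about 12%, against 16.2% with linear time.
- Two visits only: n(J − 1) − 1 = 39, so the model variance factor is 1 + x × 39/39 = 1 + x, and R = 1. Slope variation causes no inflation.

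**Step 5: detectable effect with the correct variance, visits 0-26.** Multiply 0.576 by √(1 + x). This gives 0.586, 0.617 and 0.727 at slope SD 0.25, 0.5 and 1.0. Power at 0.6 falls from 83% to 82%, 78% and 64%.

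**The case against.** Several stronger readings are tempting, and the documents do not support them.

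- *The 5% level is not held.* This needs a slope SD, and the plan gives none. At 0.25 on visits 0-26 the error is 5.3%, which is negligible. The large figures need slope SDs of 1.0 or more, or the post-study visit. An SD of 1.5 is 2.5 times the plan's own 0.6 effect.
- *A null programme is declared beneficial more than 5% of the time.* With a two-sided test only about half of the false rejections point that way. On visits 0-26 that share passes 5% only above slope SD 1.0. Sidedness is unstated. For a one-sided 5% test at slope SD 1.0, Φ(−1.645 × 0.848) is about 8%.
- *The random-intercept model is the chosen primary analysis.* It is an example in a power paragraph, with GEE beside it, and the analysis bullet defers to Aim 2 text that is not available. It is still one of only two longitudinal models that the document names.
- *Time is a straight line.* A single time term suggests this, but the coding is not given, and the paragraph also speaks of pre/post measures. Step 4 shows how far the answer depends on it.
- *GEE is free of the fault.* That holds only with robust standard errors. With a model-based exchangeable variance and balanced data it behaves like the random-intercept model.
- *The sponsor's simulation set slope variation to zero.* The 0.6 is reproduced that way, but 0.586 and 0.617 also round to 0.6. The calculation cannot show what was assumed, only that 0.6 does not survive a large slope SD.

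The strongest remaining argument is that Aim 3 is an exploratory pilot with no decision rule tied to this p-value. That lowers the priority but does not remove the point. The plan itself claims a 5% level and uses the result to judge whether the larger study should go ahead.

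**Conclusion.** The concern holds in conditional form. The named random-intercept model makes no allowance for differing rates of change. With a linear time term over five or six visits, real variation in rates makes its standard error too small: by about 15% (visits 0-26) or 29% (visits 0-38) at an assumed slope SD of 1.0, and by about 1% or 4% at 0.25. The corresponding two-sided type I errors are about 10% or 16%, and 5% or 6%. These figures assume complete data, normal errors and a slope SD that the documents do not supply.

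The near-5% benchmark comes from a t test on participant slopes, not from a fitted Kenward-Roger model. A coarse check of fitted models (300 runs, Monte Carlo error 1.5-2 points, frequent convergence warnings) at slope SD 1.0 on visits 0-26 gave 12.7% for random intercept, 7.7% for random slope and 8.0% for GEE. The ordering is clear, but a small-sample correction is needed as well. The matter is worth correcting before analysis, in proportion to a pilot.

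**What to change.** In the Aim 3 text, state how time is coded, whether the post-study visit enters the time term, and whether the test is one- or two-sided. If time is linear, name one primary method:

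- a participant random intercept and random slope with Kenward-Roger degrees of freedom, falling back to a t test on participant-level slopes if the model does not converge; or
- GEE clustered on participant with a small-sample-corrected sandwich variance.

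An unstructured covariance is less suitable: six visits need 6 × 7 / 2 = 21 parameters from 40 people or fewer.

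Re-run the Monte Carlo under the chosen method over a range of slope SDs, restate the detectable effect, and report the simulation inputs. The cost is some wording and one simulation. The downsides are a somewhat less favourable detectable effect and the need to specify a convergence fallback. The random-slope option also yields an estimate of the slope variance, which is useful for planning the larger trial.
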